3.3. Endpoints

3.3.1. Efficacy Endpoints

The efficacy data summary will include the following endpoints:

- 1) Change from baseline in metHb after the first dose of ProvayBlue™ infusion.
The primary efficacy will be the number (%) patients with $\geq 50\%$ reduction in metHb based on the first available posttreatment assessment.
 - The following are secondary endpoints to support the primary endpoint.
 - i. Change in metHb posttreatment over time
 - ii. Time when 50% reduction in metHb is observed for the first time.
- 2) Change from baseline in vital signs (blood pressure, respiratory rate, and heart rate) after the first dose of ProvayBlue™ infusion.
 - The secondary efficacy will be the number (%) of patients with concomitant normalization of vital signs within 2 hours, inclusive, after the end of infusion of the first dose of ProvayBlue™
 - Time (hours) when the first incidence of normal vital signs was observed in patients who had abnormal baseline vital signs
- 3) In addition, 13 prespecified clinical signs and symptoms associated with methemoglobinemia and their intensity (as National Cancer Institute Common Terminology Criteria for Adverse Events [NCI-CTCAE] grade) before and after ProvayBlue™ treatment are collected. The presence/absence of those signs and symptoms will be treated as an 'other' efficacy endpoint since decrease and/or resolution of those signs and symptoms may be considered supportive of efficacy.

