6.5. PROVAYBLUETM

ProvayBlueTM is an oxidation-reduction agent indicated for the treatment of pediatric and adult patients with acquired methemoglobinemia (refer to APPENDIX 1: US Package Insert of ProvayBlueTM).

Methylene blue is a water soluble thiazine dye that promotes a non-enzymatic redox conversion of metHb to hemoglobin. *In situ*, methylene blue is first converted to leucomethylene blue (LMB) via nicotinamide adenine dinucleotide phosphate (NADPH) reductase. It is the LMB molecule which then reduces the ferric iron of metHb to the ferrous state of normal hemoglobin.

The efficacy of ProvayBlueTM was assessed on the basis of a metHb decrease of at least 50% within 1 hour after intravenous (IV) administration of 1–2 mg/kg ProvayBlueTM (or a bioequivalent formulation) in 6 patients identified by retrospective chart review or literature search. All 6 patients had a decrease in metHb by at least 50% within 1 hour after treatment.

An additional 41 cases of treatment of methemoglobinemia with a methylene blue class product were identified in the published literature. Of these 41 patients, 37 (90%) had a metHb decrease of at least 50% within 1 hour after intravenous administration of the methylene blue class product.

In a combined analysis of all 47 patients treated intravenously with ProvayBlueTM (or a bioequivalent formulation) or with another methylene blue class product, there was no difference in response rate by dose. The metHb decreased by at least 50% within 1 hour of infusion for 15/17 (88%) of patients treated with 1 mg/kg, 12/13 (92%) treated with 2 mg/kg and 16/17 (94%) treated with a different dose or for those whose dose was not reported.

Refer to APPENDIX 1: US Package Insert of ProvayBlueTM for adverse reactions, clinical pharmacology and non-clinical toxicology information associate with ProvayBlueTM.

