7. STUDY OBJECTIVES AND ENDPOINTS

7.1. STUDY OBJECTIVES

7.1.1. Primary Objective

• To confirm that ProvayBlueTM after a single administration is efficacious in patients with acquired methemoglobinemia.

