7.2. STUDY ENDPOINTS

7.2.1. Primary Efficacy Endpoint

• A 50% reduction in metHb level within 1 hour of the first dose of ProvayBlueTM for treatment of acquired methemoglobinemia.

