12.2. TREATMENT

Due to the nature of the disease indication, the patient's treatment with ProvayBlueTM as per standard of care can take place prior to or after PICD signature. Data collection (retrospective and prospective) for this study and study specific assessments will only take place after PICD signature.

Refer to APPENDIX 2: Study Flow Chart for data collection time points and schedule of assessments.

Assessments during treatment and the relevant collection of data (as per standard of care) include the following:

- ProvayBlueTM administration (including dose, lot number, date, time and route of administration, and if any dilution took place);
- Clinical symptoms related to methemoglobinemia and severity:
 - Within 1 hour after the end of each ProvayBlueTM infusion (i.e. both Dose 1, Dose 2 and any additional dose if applicable);

- Within 2 hours after the end of each ProvayBlue[™] infusion (i.e. both Dose 1, Dose 2 and any additional dose if applicable);
- Approximately 24 hours post the end of the last ProvayBlueTM infusion, or just prior to discharge from the clinic if earlier than 24 hours.
- Vital signs (refer to Section 15.2.2 for the list of parameters):
 - o Within 1 hour after the end of each ProvayBlue[™] infusion (i.e. both Dose 1, Dose 2 and any additional dose if applicable);
 - o Within 2 hours after the end of each ProvayBlue™ infusion (i.e. both Dose 1, Dose 2 and any additional dose if applicable);
 - o Approximately 24 hours post the end of the last ProvayBlue™ infusion, or just prior to discharge from the clinic if earlier than 24 hours.
- Blood sample for:
 - o Biochemistry, hematology and metHb (refer to Section 15.2):
 - Within 1 hour after the end of each ProvayBlueTM Dose 1 infusion (i.e. Dose 1, Dose 2 and any additional dose if applicable);
 - Prior to ProvayBlueTM Dose 2 if applicable (i.e., if the metHb level is acceptable within 1 hour after the end of Dose 1 ProvayBlueTM infusion, the repeat dose of ProvayBlueTM will not be needed);
 - Approximately 24 hours post the end of the last ProvayBlueTM infusion, or just prior to discharge from the clinic if earlier than 24 hours.
 - o PK analysis (refer to Section 14):
 - Approximately 1 hour after the end of each ProvayBlueTM infusion (i.e. Dose 1, Dose 2 and any additional dose if applicable);
 - Prior to Dose 2 (or any additional dose) ProvayBlueTM infusion (if applicable);

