13.2. METHODS AND TIMING FOR ASSESSING, RECORDING AND ANALYSING EFFICACY PARAMETERS

The primary endpoint is assessed over a period of 1 hour after administration of the first dose of ProvayBlueTM. The secondary endpoints are assessed over a period of 2 hours after administration of each dose of ProvayBlueTM.

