16.2.1. General Considerations

Continuous variables will be summarized by descriptive statistics (number of patients, mean, standard deviation [SD], minimum, median and maximum). Geometric mean and coefficient of variation (CV) will be presented for PK parameters when appropriate. Categorical data will be summarized by absolute and relative frequencies.

A 95% confidence interval (CI) for the responder rate will be presented for each of the primary and secondary endpoints.

All variables will be listed on a patient level.

Unless indicated otherwise, summary statistics will be reported for observed data only. Missing data will not be imputed. If a baseline value is missing, no change from baseline will be calculated.

Baseline for all assessments will be defined as the last measurement taken prior to dosing with study drug.

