16.4. EVALUATION OF EFFICACY

Refer to Sections 7.2.1 and 7.2.2 for the primary and secondary efficacy endpoints, respectively.

Efficacy evaluations will be performed using the FAS.

Efficacy will be assessed based on the metHb level and on the normalization of respiratory rate, heart rate and blood pressure after administration of ProvayBlueTM (single- or repeat dose).

The results will be descriptive only. A 95% CI for the responder rate will be presented for each of the primary and secondary endpoints. The results will be compared with historical methylene blue results to confirm that ProvayBlueTM's results are not unexpected.

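### The SAP's primary counts a 50% metHb fall at the first available sample, with no time limit, no rule for samples after re-dosing, and no table specified to report it

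*SAP*

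**What the plan says.** **Endpoint.** SAP 3.3.1, under an item on change after the first dose, defines the primary as the number (%) of patients with at least a 50% "reduction in metHb based on the first available posttreatment assessment". The title of Table 14.2.1.2 (SAP 7.1) confirms that sample timing is ignored. SAP 5.1.1 gives the reason: post-dose assays may come hours after the infusion, and the Observational Study has no sampling schedule. The same section defines metHb_1, the input to the 1-hour prediction, simply as the first post-treatment value.

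**Protocol.** The primary endpoint in 7.2.1 is "A 50% reduction in metHb level within 1 hour of the first dose", and 13.2 adds: "The primary endpoint is assessed over a period of 1 hour after administration of the first dose". The objective in 7.1.1 is to confirm that the product "after a single administration is efficacious in patients with acquired methemoglobinemia". SAP Table 1 still lists the 1-hour endpoint for the Interventional Study.

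**Re-dosing.** Protocol 8.1 and footnote p of SAP Table 2 allow a repeat dose 1 hour after the first, either for metHb still above 30% or for persisting signs and symptoms. For the Interventional Study, Protocol 12.2 schedules a metHb sample "Prior to ProvayBlueTM Dose 2 if applicable".

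**Tables (SAP 5.1.3).** Table 14.2.1.1 reports responders at 1 hour from the predicted value, in patients first sampled before 2 hours. Table 14.2.1.2 covers first follow-up samples in the whole efficacy set; its described content is metHb level and sampling time.

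**The concern.** The objective concerns a single administration. A responder rule that accepts the first sample whenever it was drawn can count a fall that appeared hours later, or that followed a second dose or another treatment. The error can also run the other way: SAP 3.7.2 expects continuing metHb production with dapsone, so a late first sample can miss a response that had occurred by 1 hour.

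Two consequences follow. The headline percentage could be read as a first-dose, 1-hour result when it is neither. And since no table is specified to hold that percentage, the only responder percentage a reader is certain to see is a linear projection in a subset.

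**Working it through.** **Inputs.** Enrolment is 7 (Interventional) and 24 (Observational), from SAP section 1. The worked example and the 2-hour restriction come from SAP 5.1.1. Efficacy-set size, first-sample times and the number re-dosed before sampling are not given.

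**1. The SAP's own example.** Baseline is 74.4 and the first sample is 15.7 at 70 min. I follow the arithmetic of the worked lines.
- Predicted 1-hour level: 74.4 + 60 × (15.7 − 74.4)/70 = 24.09, as stated.
- Predicted 1-hour change: 100 × 60 × (15.7 − 74.4)/70/74.4 = −67.63%, as stated.
- Change on the 3.3.1 primary: 100 × (15.7 − 74.4)/74.4 = −78.9%.

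This patient responds on both counts, but the two measures differ.

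**2. Can the predicted rate stand in for the primary?** Let F be the % fall at the first sample, at t minutes (t < 120). The predicted 1-hour fall is F × 60/t.
- F = 55 at 90 min: 55 × 60/90 = 36.7%. Responder on the primary, not on the prediction.
- F = 35 at 30 min: 35 × 60/30 = 70.0%. Non-responder on the primary, responder on the prediction.

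The second case is a forward extrapolation, not an observation. So the planned 1-hour rate replaces neither the primary nor an observed within-1-hour rate.

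**3. Effect of lateness alone.** Assume the SAP's linear fall and a time T50 to a 50% fall. The fall at t is 50 × t/T50, capped at 100%.

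| Assumed T50 | Fall at 1 h | Fall at 2 h | Fall at 3 h |
|---|---|---|---|
| 90 min | 33% | 67% | 100% |
| 120 min | 25% | 50% | 75% |

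Both patients miss 50% at 1 hour, and both count as responders if first sampled at 2 or 3 hours. No second dose is needed.

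**4. Re-dosing.** In the Interventional Study the scheduled pre-Dose 2 sample should normally supply a clean first value. The exposure is mainly in the registry. If registry practice resembles the interventional text (an assumption, since its protocol is not provided), a patient could be re-dosed on symptoms alone with no metHb in between. Neither 3.3.1 nor 5.1.1 says how that patient counts. The 2-hour limit in 5.1.1 does not close the gap, because a sample between 1 and 2 hours can follow a repeat dose given at 1 hour.

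**5. Size per patient.** The efficacy set holds at most 7 + 24 = 31, and fewer once Secondary cases and patients without paired metHb are removed. One patient is worth at least 100/31 = 3.2 points (100/20 = 5.0 if N = 20, assumed). With assumed counts, 28/31 = 90.3% (exact 95% CI 74.3 to 98.0) becomes 25/31 = 80.6% (62.5 to 92.6) if three patients are reclassified.

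**6. Why the denominator must be stated.** Take 18/20 = 90.0% as written, with two patients first sampled after re-dosing, one of them counted as a responder (all assumed). Keeping both in the denominator as not shown to respond gives 17/20 = 85.0%. Excluding both gives 17/18 = 94.4%. A bare instruction not to credit such samples could therefore raise the rate.

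**The case against.** The case for leaving the plan alone is substantial, and much of it stands.

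- The open timing is disclosed and reasoned, and Table 14.2.1.2 shows sampling time beside level. The endpoint heading names the first dose. This stands: what is missing is an operating rule, not the intent.
- A 1-hour responder count is already planned. This stands in part: it is predicted, and restricted to first samples before 2 hours.
- A reader might infer that the SAP wrongly overrides a protocol endpoint outside the superseded statistical section. The documents do not support that firmly. SAP section 1 supersedes the protocols' statistical sections, and Protocol 16.4, inside that section, incorporates 7.2.1 by reference.
- A reader might also infer that the planned historical comparison is invalid. Protocol 6.5 does give 1-hour rates ("The metHb decreased by at least 50% within 1 hour of infusion for 15/17 (88%) of patients treated with 1 mg/kg"), and Protocol 16.4 says: "The results will be compared with historical methylene blue results". But the SAP plans no such comparison, so the point applies only if one is made.
- The general provisions in SAP 3.4 and section 4 for confidence intervals and number (%), each where appropriate, could produce the missing row. They could, but they assign it to no table.
- The report is descriptive, with metHb profiles for every patient (5.1.4) and listings of dosing and derived metHb values (7.2). This stands, and it lowers the severity.

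**Conclusion.** The gap is real but modest. SAP 3.3.1 leaves sample time unlimited and is silent on a first sample drawn after re-dosing or other treatment, 5.1.1 shares that silence, and no table is specified for the declared primary. The result could be a headline rate read as a first-dose, 1-hour effect when it is not.

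Two stronger readings go beyond the documents. One is that the rate will be inflated: the direction is open, the number affected cannot be computed and may be zero, and the re-dose route rests on an assumption about registry practice. The other is that the 1-hour endpoint has been dropped or data concealed: a predicted 1-hour rate and patient-level displays are both planned.

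Severity: minor to moderate.

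**What to change.** 1. In SAP 3.3.1 and 5.1.1, use only metHb samples taken before any second dose or other recorded methemoglobinemia treatment. Keep patients with no such sample in the denominator as not shown to respond to the first dose, and give the rate with them excluded as a sensitivity analysis. Report their number, and the number whose sample order cannot be determined.
2. Add to Table 14.2.1.2 the number (%) with at least 50% reduction, with a 95% CI.
3. Beside it, report the observed rate within 1 hour of the first dose and the number not sampled in that window. Protocol 16.2.1 states "Missing data will not be imputed", so a patient first sampled later has no observed value. Label the Table 14.2.1.1 rate as predicted. If any comparison with the historical 1-hour rates is made, use the observed 1-hour rate, not the any-time first-sample rate.

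**Cost.** SAP wording and a few table rows, from domains already planned in SAP Table 3 (EX, CM, LB). SAP 3.3.2 imputes only a missing stop time for the first infusion, so some sample orders may be undeterminable; count these rather than assume an order. The headline rate may be less favourable, and few patients may have an observed 1-hour value.

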3.2. Analysis Population

The following analysis sets will be identified for data summary.

Enrolled Analysis Set: All patients who sign the informed consent or otherwise meet all local enrollment criteria for the study are considered to have enrolled.

Safety Analysis Set: The safety set will include all enrolled patients who are treated with at least 1 ProvayBlue™ infusion dose. The safety analysis set will be used for safety data summary. Specifically, the safety population will include all treated patients from the Interventional Study and the Observational Study.

Efficacy Analysis Set: The efficacy analysis set includes all safety analysis set patients who have at least 1 metHb assessment before and after ProvayBlue™ infusion and who are Primary cases. This analysis set will be used for efficacy endpoint evaluation.

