3.3.2. Relative Time of Efficacy Endpoints

A relative time frame will be used to display and to summarize efficacy assessments.

The stop time of the first ProvayBlue™ infusion will be used to derive relative time (hours) for each post infusion metHb and vital signs assessment. After all efforts are made to ensure the capture of infusion start and stop time, when the stop time is missing, the following imputation rule will be used to impute the missing stop time.

Missing stop time will be imputed with the median infusion duration of the efficacy population. Mathematically, this imputation rule can be expressed as

$$\text{Stop time} = \text{start time} + \text{median infusion duration}$$

Where the median infusion duration is derived from all patients in the efficacy population.

Relative time of an assessment (hours) = Time of assessment – Time of stop time of 1st Infusion.

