5.1.1. MetHb Level at 1-hour Post Dosing

The timing of postdosing metHb level assays is inconsistent in clinical practice and may not be obtained until hours after the conclusion of first dose infusion in the emergency department. It should be noted that, consistent with such practice, the Observational Study does not have a prespecified schedule for metHb postdosing collection. MetHb level at 1-hour postdosing will be derived using linear interpolation. This method will be referred to as backward linear interpolation if the first postdosing metHb was after 1 hour, or forward linear interpolation if the first postdosing metHb was before 1 hour. This method will be mathematically expressed as follows.

Step 1: calculate rate of metHb change per minutes)

$$= (\text{metHb_1} - \text{baseline}) / \text{time of metHb_1 in minutes}$$

Step 2:

$$\text{metHb_1hr} = \text{baseline} + 60 * [(\text{metHb_1} - \text{baseline}) / (\text{time of metHb_1 in minutes})]$$

where

- baseline = baseline metHb defined as the last metHb before the first dose of study drug)
- metHb_1 = first post treatment metHb observation
- constant (60) converted the time units from minutes to hours

For example, a patient has metHb of 74.40 at baseline and 15.70 at 70 minutes postdosing. The estimated metHb_1hr is 24.08571.

Percent change from baseline (PCHG) at 1-hour post dosing can be estimated as follows.

$$\text{PCHG (\%)} \text{ at 1-hour post dosing} = 100 * [(\text{metHb_1} - \text{baseline}) / \text{time of metHb_1 in minutes}] / \text{baseline}$$

The PCHG for the above example is -67.63%.

$$\text{PCHG at 1-hour} = 100 * \{ [60 * (15.7 - 74.4) / 70] / 74.4 \}$$

Due to the mathematical property of this derivation, a patient could never achieve 50% reduction at 1-hour post dosing if the first postdosing metHb was taken after 2 hours. Hence, this derivation will be applied only to those patients who had first postdosing metHb before 2 hours.

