5.1.2. Time When metHb Level Reached 50% Reduction

To estimate the time when a 50% reduction would be obtained, the following linear interpolation will be applied.

$T_{50} \text{ (minutes after first dose)} = (\text{baseline}/2) / [60 * (\text{baseline} - \text{metHb}_1) / \text{time of metHb}_1 \text{ in minutes}]$

T50 for the above example is 44 minutes.

$$T_{50} = (74/2) / \{ [(74.4 - 15.7) / 70] / 74.4 \} = 37.2 / 0.838571428 = 44.36$$

The units for T50 will be converted to hours by $T_{50} / 60$ in the dataset.

Due to the mathematical property of this derivation, a patient could never achieve 50% reduction at 1-hour post dosing if the first postdosing metHb was taken after 2 hours. Hence, this derivation will be applied only to those patients who had first postdosing metHb before 2 hours.

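### The SAP's first-dose primary endpoint has no Dose 2 cut-off, so a patient re-dosed before any post-dose metHb draw has a two-dose result credited to the first dose

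*SAP*

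**What the plan says.** SAP section 3.3.1 heads the endpoint "Change from baseline in metHb after the first dose of" the drug, then defines the primary result as the number and percentage of patients with a 50% or greater "reduction in metHb based on the first available posttreatment assessment". No time limit is attached. Table 14.2.1.2 is titled as covering the first follow-up metHb whenever it was taken.

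The efficacy set (SAP 3.2) consists of Primary cases "who have at least 1 metHb assessment before and after" infusion, with no condition on the number of doses. Under SAP 3.3.2 the stop time of the first infusion "will be used to derive relative time (hours) for each post infusion metHb and vital signs assessment"; later infusions do not reset or stop that clock.

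SAP 5.1.1 estimates metHb at 1 hour on a straight line from baseline through the first post-dose value, and "this derivation will be applied only to those patients who had first postdosing metHb before 2 hours". SAP 5.1.2 uses the same line, with the same 2-hour restriction, to obtain T50, the time to a 50% fall.

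On timing of draws, SAP 5.1.1 says that the first post-dose metHb "may not be obtained until hours after the conclusion of first dose infusion in the emergency department", and that "the Observational Study does not have a prespecified schedule for metHb postdosing collection".

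On dosing, protocol section 8.1 allows a repeat dose 1 hour after the first if metHb stays above 30% or if signs and symptoms persist. Protocol section 12.2 schedules metHb within 1 hour after the end of Dose 1 and again before Dose 2, but only for the Interventional Study.

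**The concern.** The heading attributes the effect to one dose, while the scoring rule takes whichever value comes first, however many doses preceded it. In most patients the two should agree, because the first draw should come before any second dose. They part when a patient is re-dosed, perhaps on symptoms alone, and the first post-dose metHb is drawn only afterwards. That value reflects two doses but is scored as the result of one.

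The Interventional Study's primary objective is efficacy after a single administration (protocol 7.1.1), and the pooled report is meant to satisfy a post-marketing requirement (SAP 1). A reader of the headline rate will take it as a single-dose rate. Re-dosing is most plausible in the dapsone group, where SAP 3.7.2 expects metHb production to continue during treatment. Summary tables are split by that grouping, so one patient weighs more there.

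**Working it through.** **Is there a Dose 2 rule anywhere?** SAP 3.2 (efficacy set), 3.3.2 (relative time), 3.5 (missing data) and 5.1.1 to 5.1.4 (metHb derivations) contain none. The number of doses is used only in the exposure table (SAP 6.1). The protocol's 1-hour window (7.2.1) is not carried into the SAP's scoring rule, and the SAP states that it supersedes the protocols' statistical sections.

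**The plan's own example.** Baseline is 74.4 and metHb is 15.7 at 70 minutes.
- 1-hour value: 74.4 + 60 × (15.7 − 74.4)/70 = 24.09.
- Percent change: 100 × [60 × (15.7 − 74.4)/70]/74.4 = −67.63%.
- T50: 37.2/[(74.4 − 15.7)/70] = 44.36 minutes.

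All three agree with the SAP's results. With F the percent fall at the first draw and t its time in minutes, the line reduces to:
- estimated 1-hour fall = 60 × F/t
- T50 = 50 × t/F

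**Can two doses make a responder when one would not?** Assume that each dose removes a fixed share d of the remaining metHb. The two-dose fall is 1 − (1 − d)². With d = 30% it is 51%; with d = 45% it is 69.75%. Any d from 29.3% up to, but not including, 50% fails after one dose and passes after two.

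**Does the 2-hour restriction prevent this?** It does not touch the first-available count. For the interpolated rate it makes misclassification harder without excluding it. A draw at time t counts as a response only if F is at least 50 × t/60: 58.3% at 70 minutes, 75.0% at 90 and 83.3% at 100.

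Illustration on assumed values: Dose 1 gives a 45% fall at 1 hour, Dose 2 follows, and the first draw at 75 minutes shows a 65% fall.
- Estimated 1-hour fall: 60 × 65/75 = 52.0%, a responder.
- T50: 50 × 75/65 = 57.7 minutes, a time before Dose 2 was given.
- If Dose 1 had simply continued on its line, the fall at 75 minutes would have been 45 × 75/60 = 56.25%, which returns 45.0%, a non-responder.

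**Direction.** 60 × F/t increases with F, so a Dose 2 that lowers metHb can only raise the estimated fall (and shorten T50). The first-available fall is F itself, so it moves the same way.

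**Size.** Enrolled: 7 + 24 = 31, which is the ceiling for the efficacy set; its actual size is not given. The Observational share is 24/31 = 77.4%. Assume 28/31 as written, with every affected patient scored a responder. Intervals are exact 95%.

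| Affected patients | Excluded | Kept as not shown |
|---|---|---|
| 0 | 28/31 = 90.3% (74.2–98.0) | same |
| 1 | 27/30 = 90.0% (73.5–97.9) | 27/31 = 87.1% (70.2–96.4) |
| 3 | 25/28 = 89.3% (71.8–97.7) | 25/31 = 80.6% (62.5–92.5) |

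The changes are 0.3 and 3.2 points for one patient, and 1.0 and 9.7 points for three. In a subgroup of 15 (assumed size), one patient kept as not shown is worth 1/15 = 6.7 points.

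**The case against.** The case is narrow. It needs a second dose with no metHb since the first, although the label asks clinicians to monitor metHb during treatment and bases re-dosing partly on the level. The Interventional Study, whose objective specifies a single administration, schedules the draws that close the gap; the Observational Study's stated objective does not mention a single dose. The heading could also be read as fixing the start of the clock rather than attributing the effect. The summary is descriptive, no decision rule depends on the rate, and narratives, profiles and listings would let a careful reader find such a patient.

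Most of this stands and limits the weight of the point. It does not remove it. Re-dosing on symptoms alone is allowed, the SAP itself expects late first draws, and the pooled endpoint carries the first-dose heading for both studies. Being able to trace a case in a listing does not correct the reported count.

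A reader might infer more than the documents support in three ways.
- *Every re-dosed patient is miscounted.* No: taking the first available value protects anyone sampled before Dose 2.
- *Every affected patient is a false responder.* No: a post-Dose-2 fall below 50% is scored as non-response, and some patients above 50% might have got there on Dose 1 alone.
- *The interpolated rate can err in either direction because of Dose 2.* Suppose a true 1-hour fall of 55% and a first draw at 90 minutes showing 70%. The line gives 60 × 70/90 = 46.7%, a wrong non-response. But without Dose 2 the fall at 90 minutes would have been no larger, so the estimate would still be 46.7% or less. That error comes from the straight-line assumption, which is a separate matter.

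**Conclusion.** The point holds as a gap in the endpoint rule. Applied literally, the SAP credits a two-dose outcome to the first dose in any patient whose first post-dose metHb follows Dose 2. The resulting bias is upward so far as Dose 2 lowers metHb.

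The documents do not show that the reported rate is in fact inflated: the number of such patients is not given and may be zero. The sizes above rest on an assumed 28/31, on assumed counts of one and three, and on all of them being scored responders. The larger figures apply only when affected patients stay in the denominator; exclusion barely moves the estimate. The rule should be corrected because doing so is cheap and settles what the headline rate means, not because a large error has been demonstrated.

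**What to change.** Amend the SAP only, before database lock.

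1. For the responder count, the 1-hour estimate and T50, use only metHb drawn after Dose 1 and before the recorded start of Dose 2.
2. Flag each patient whose first posttreatment metHb follows Dose 2, and state how many there are. If there are none, one sentence closes the question.
3. Report the responder rate side by side with flagged patients excluded, and with them kept in the denominator as not shown to be single-dose responders. The second is a lower bound with respect to these patients, not a claim that they failed.

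The cost is one derivation rule, one flag and an added row in Tables 14.2.1.1 and 14.2.1.2. SAP 5.1.3 does not list a responder count among the contents of Table 14.2.1.2, so that count should be added there too. No new patients, visits or procedures are needed.

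There are two limits. A few patients may be left with no evaluable single-dose value. The rule also depends on Dose 2 start times having been recorded in the Observational Study: SAP 3.1 lists drug administration among the pooled data, but that study's protocol and CRF are not among the documents, so this should be confirmed first.
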